7.3 Study Population

7.3.1 Participant Disposition

Participant disposition will be listed. Summary tables reflecting the number of participants who are enrolled, who are randomized, who are not randomized, and reasons for not being randomized will be presented as overall for the enrolled population.

The number of participants who complete the study, who do not complete the study, and reasons for not completing the study, will be summarized for the treated population, as overall and by treatment sequence.

7.3.2 Demographic Characteristics

Demographic characteristics such as gender, age, race, and ethnicity will be listed for the treated population. Demographic characteristics will also be summarized for the treated population, as overall and by treatment sequence.

7.3.3 Physical Measurements

Physical measurements such as body weight, height, and body mass index (BMI) will be listed for the treated population. Measurements will also be summarized by nominal visit for the treated population, as overall and by treatment sequence.

7.3.4 Medical History and Previous Medications

Medical history and previous medications taken prior to dosing will be listed for the treated population.

7.4 Extent of Exposure

No analysis regarding extent of exposure is planned. Randomization schedule will be listed for the randomized population. Study drug administration and batch numbers will be listed for the treated population. Any non-study medications taken by participants, any non-study medical treatment procedures conducted, and any non-study diagnostic procedures utilized will also be listed for the treated population.

7.5 Efficacy

There are no efficacy assessments in the study.

7.6 Safety

Analysis of all safety data will follow the BMS guideline of analysis of safety data. The evaluation of safety is based on clinical AEs, vital signs, ECG results, clinical laboratory results, and abnormal physical examinations reported during the study.

Unless otherwise specified, all safety presentations will utilize the treated population as described in [Section 6.3](#).

All data collected from the sampling outside the scheduled visits will only be included in the listing and will be excluded from the summary tables.

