| Clinical Laboratory Tests | | | | X | | | X | | Includes blood and urine samples. Full clinical laboratory tests will be done including coagulation parameters (aPTT, INR, and PT) will be measured on Days 4 and 7. Results of clinical laboratory tests performed on Day 4 must be available prior to dosing on Day 5. See note in screening procedures and Section 9.4.4 . |
| Pregnancy Test (serum) | | | | X | | | X | | Serum pregnancy testing must be done within approximately 24 hours of Day 5. Results must be reviewed prior to dosing on Day 5. Serum pregnancy tests must be reported in a quantitative result. |

Table 2-2: On Treatment Procedural Outline (CV185687)

| Procedure | D1 | D2 | D3 | D4 | D5 | D6 | D7 | D8 (Study Discharge) ^a | Notes |
|--------------------------------|----|----|----|----|----|----|----|--------------------------------------|---|
| Adverse Event Reporting | | | | | | | | | |
| Monitor for Nonserious AEs | X | X | X | X | X | X | X | X | Nonserious AEs will be collected from the initiation of study treatment (Day 1) until 3 days after the last dose of study treatment. |
| Monitor for SAEs | X | X | X | X | X | X | X | X | See note in screening procedures. |
| PK Assessments | | | | | | | | | See Table 9.5-1 . An additional PK sample may be collected in the event of discontinuation due to an AE. |
| Serial Blood PK Sampling | X | X | X | X | X | X | X | X | See Section 9.5 . |
| Clinical Drug Supplies | | | | | | | | | |
| Randomize | X | | | | | | | | Randomization will occur prior to study drug administration. |
| Apixaban Administration | X | | | | X | | | | See Section 7 . |
| Other Assessments | | | | | | | | | |
| Palatability Assessment | X | | | | X | | | | For both treatments. Palatability assessment will be completed immediately (within 5 minutes) after administration of the apixaban 0.5-mg tablet and 0.1-mg sprinkle capsule dosages. Refer to Appendix 6 . |

^a Evaluations performed prior to study discharge or for participants who are prematurely discontinued.

AE = adverse event; aPTT = activated partial thromboplastin time; D = Day; ECG = electrocardiogram; INR = international normalized ratio; PK = pharmacokinetic; PT = prothrombin time; SAE = serious adverse event

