9.2.7 Potential Drug-Induced Liver Injury (DILI)

Wherever possible, timely confirmation of initial liver-related laboratory abnormalities should occur prior to the reporting of a potential drug-induced liver injury (DILI) event. All occurrences of potential DILIs, meeting the defined criteria, must be reported as SAEs (see [Section 9.2](#) and [Appendix 3](#) for reporting details).

Potential DILI is defined as:

- 1) Aminotransaminases (ALT or AST) elevation > 3 times ULN
AND
- 2) Total bilirubin > 2 times ULN, without initial findings of cholestasis (elevated serum alkaline phosphatase),
AND
- 3) No other immediately apparent possible causes of aminotransaminases elevation and hyperbilirubinemia, including, but not limited to, viral hepatitis, pre-existing chronic or acute liver disease, or the administration of other drug(s) known to be hepatotoxic.

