9.4.4 Clinical Safety Laboratory Assessments

Investigators must document their review of each laboratory safety report.

A local laboratory will perform the analyses and will provide reference ranges for these tests.

Results of clinical laboratory tests performed on Day -1 and Day 4 must be available prior to dosing on Days 1 and 5, respectively.

| | |
|--|----------------------------------|
| Hematology | |
| Hemoglobin | |
| Hematocrit | |
| Total leukocyte count, including differential | |
| Platelet count | |
| Coagulation (at screening, Day -1, Day 4, and Day 7) | |
| aPTT | |
| INR | |
| PT | |
| Serum Chemistry | |
| AST | Total Protein |
| ALT | Albumin |
| Total bilirubin | Sodium |
| Direct bilirubin (reflex if elevated total bilirubin) | Potassium |
| Alkaline phosphatase | Chloride |
| Lactate dehydrogenase | Calcium |
| Creatinine | Phosphorus |
| Blood Urea Nitrogen | Creatine kinase (screening only) |
| Uric acid (screening only) | |
| Fasting glucose | |
| Urinalysis | |
| Protein | |
| Glucose | |
| Blood | |
| Leukocyte esterase | |
| Specific gravity | |
| pH | |
| Microscopic examination of the sediment if blood is detected on the initial analysis | |
| Serology | |
| Serum hepatitis C antibody, hepatitis B surface antigen, HIV-1 or -2 antibody (screening only) | |
| Other Analyses | |
| Urine for drugs of abuse including cotinine and alcohol (screening and Day -1) | |
| Serum pregnancy test (women only: at screening, Day -1, Day 4, and Day 7) | |
| Serum follicle-stimulating hormone (postmenopausal women only; screening) | |

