6 STUDY PERIODS, TREATMENT REGIMENS AND POPULATIONS FOR ANALYSES

6.1 Study Periods

- The pre-treatment period will be from the time the Informed Consent Form (ICF) is signed until the time just prior to dosing on Day 1 for all participants. The pre-treatment period should be no longer than 28 days and will include all screening, enrollment, Day -1, randomization, and Day 1 predose procedures.
- Period 1 will be from the time of dosing on Day 1 until the time prior to dosing in the next period on Day 5, or until study discharge due to premature discontinuation if the participant is not dosed on Day 5.
- Period 2 will be from the time of dosing on Day 5 until the participant is discharged on Day 8, or until the day of study discharge due to premature discontinuation after dosing on Day 5.
- If a participant is not discharged on Day 8, any data collected after Day 8 will be assigned to the post-treatment period.
- Periods 1 and 2 will be considered on-therapy for the purpose of safety analyses.

The definition of each study period is included in [Table 6.1-1](#).

Table 6.1-1 Definition of Study Period

PERIOD SEQUENCE	PERIOD NAME	DATE TO BE USED	DEFINITION
1	PRE-TREATMENT	- CONSENT DATE - DOSE DATETIME ON DAY 1	Starting with consent date and ending by (<) dose date and time on Day 1
2	PERIOD 1	- DOSE DATETIME ON DAY 1 - DOSE DATETIME ON DAY 5	Starting with dose date and time on Day 1 and ending by (<) dose date and time on Day 5
3	PERIOD 2	- DOSE DATETIME ON DAY 5 - DISCHARGE DATE	Starting with dose date and time on Day 5 and ending by (≤) discharge date
4	POST-TREATMENT	- DISCHARGE DATE	Starting with discharge date + 1

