7.6.4 Clinical Laboratory Evaluations

The results of all protocol-specified clinical laboratory tests will be listed by participant for the treated population.

Laboratory evaluations will be reported both in conventional units and in International System of Units.

Laboratory results will be classified as markedly abnormal based on sponsor defined criteria. Laboratory results for participants with any marked laboratory abnormality (scheduled and unscheduled) will be listed for the treated population. This listing will include all observations for the specific laboratory test and participant, not only the marked laboratory abnormality measurements. The frequency of participants with any on-treatment marked laboratory abnormality, based on pre-specified criteria, will be presented for the treated population by treatment and total.

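### Read literally, SAP 7.6 leaves an on-treatment marked laboratory abnormality seen only on an unscheduled test out of the one laboratory summary table

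*SAP*

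**What the plan says.** - SAP 7.6 sets a general rule for safety data: results from "sampling outside the scheduled visits will only be included in the listing and will be excluded from the summary tables". An unless-otherwise-specified clause appears in the same section, but it governs only the analysis population.
- SAP 7.6.4 plans listings and one summary table. The listing covers both kinds of result: "Laboratory results for participants with any marked laboratory abnormality (scheduled and unscheduled) will be listed for the treated population". The table is described as "The frequency of participants with any on-treatment marked laboratory abnormality", for the treated population, by treatment and overall. The mention of unscheduled results is attached to the listing and not repeated for the table.
- SAP 6.1 defines the on-treatment window by time, not by visit: "Periods 1 and 2 will be considered on-therapy for the purpose of safety analyses".
- Protocol 10.3.3 says that the number and percentage with marked laboratory abnormalities will be summarized. It does not limit this to scheduled visits. SAP 4.2 names marked laboratory abnormalities as a safety endpoint.
- Protocol Table 2-2 schedules post-dose laboratory tests on two days only. Its note says "coagulation parameters (aPTT, INR, and PT) will be measured on Days 4 and 7", and Protocol 9.4.4 agrees: "Coagulation (at screening, Day -1, Day 4, and Day 7".
- Footnote a to the Day 8 column of Table 2-2 makes that column the early-discontinuation evaluation as well: "Evaluations performed prior to study discharge or for participants who are prematurely discontinued". It contains no laboratory test.

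**The concern.** The endpoint is any marked abnormality while on treatment. The general rule in SAP 7.6 reduces this to any marked abnormality on the one scheduled draw for that treatment. A for-cause test taken between draws, or a test taken when a participant leaves early, could show a marked abnormality that the table never counts.

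At stake is the completeness of the only planned laboratory table that sets the two treatments side by side. A programmer who follows the explicit exclusion will produce a narrower table than the protocol describes, and nothing on the page will show that anything was left out.

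**Working it through.** The plan gives no figure for this point, so the check is a count from the schedule followed by a comparison of the rules.

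**Inputs**

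- Doses on Days 1 and 5 (Protocol 5.1).
- Laboratory row and Day 8 column of Table 2-2.
- Period definitions (SAP 6.1).
- 30 participants planned to be randomized (Protocol 10.1).

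**Scheduled draws per treatment**

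The laboratory row is marked under Day 4 and Day 7 and nowhere else from Day 1 to Day 8.

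- Period 1: Day 1 dose to Day 5 dose = (5 − 1) × 24 = 96 h, with 1 scheduled draw. It falls nominally (4 − 1) × 24 = 72 h after dosing.
- Period 2: Day 5 dose to Day 8 discharge = (8 − 5) × 24 = 72 h nominal, with 1 scheduled draw. It falls nominally (7 − 5) × 24 = 48 h after dosing.
- Clock times for the draws are not given, so 72 h and 48 h are approximate.
- The Day 8 column has physical examination, weight, vital signs, ECG, AE monitoring and PK sampling, but 0 laboratory tests.

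A participant who leaves after the Day 1 dose but before the Day 4 draw, or after the Day 5 dose but before the Day 7 draw, therefore has no scheduled post-dose laboratory result for that treatment.

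**The rules applied to each case**

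| Where the marked result appears (Period 1 or 2) | Listed? | In the table under SAP 7.6? | Within the summary described in Protocol 10.3.3? |
|---|---|---|---|
| Scheduled Day 4 or Day 7 draw | Yes | Yes | Yes |
| Scheduled draw and a later repeat | Yes | Yes, already counted once | Yes |
| Unscheduled test only | Yes | No | Yes |
| Test at early discontinuation, scheduled draw not taken | Yes | No, since the schedule has no such test | Yes |

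The last two rows are the gap.

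**Size**

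Let k be the number of participants whose only marked abnormality on a treatment comes from an unscheduled test. The table understates that treatment's rate by k/N. The documents give no value for k, so the values below are assumed. N = 30 assumes that every planned participant receives the treatment.

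- k = 0: no effect
- k = 1: 1/30 = 3.3 percentage points
- k = 2: 2/30 = 6.7 percentage points
- k = 3: 3/30 = 10.0 percentage points

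If one participant does not receive that treatment, k = 1 gives 1/29 = 3.45 percentage points.

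**The case against.** **The sections can be read together.** SAP 7.6.4 mentions unscheduled results for the listing and not for the table, which is what an author applying SAP 7.6 would write. On-treatment can then mean just the time window. This stands as a fair reading, so a flat contradiction within the SAP is more than the text shows. It does not remove the point: on that reading the table is deliberately narrower than Protocol 10.3.3, and no reason is given.

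**Leaving out for-cause tests is defensible.** In an open-label study, extra testing may differ by treatment and distort a comparison. This has force, and it is why unscheduled-only cases should be shown separately. The table is descriptive, with no planned test, so completeness costs little.

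**Other documents may settle it.** SAP 7.6 refers to a sponsor guideline for safety data, SAP 7.9 to sponsor counting rules, and SAP 8 to a Data Presentation Plan. None is available here. Any of them could resolve the question, but the SAP text does not.

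**Stronger readings that the documents do not support**

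- A reader might infer that repeat liver tests in completers would go uncounted, because Protocol 9.2.7 says that "timely confirmation of initial liver-related laboratory abnormalities should occur prior to the reporting". The table counts participants, not results. If the scheduled value was itself marked, the participant is already counted. The repeat matters only if the scheduled value was not marked, and potential drug-induced liver injury must in any case be reported as an SAE.
- A reader might infer that the table has no stated population, or that 28 is its denominator. SAP 7.6.4 names the treated population by treatment, and 28 is the PK-evaluable target, not a safety count. What is not spelled out is whether a treated participant with no post-dose result belongs in the denominator.
- A reader might infer that a safety signal would be lost. It would not. The listing shows all observations for that participant and test, and clinically significant results are recorded as AEs (Protocol 9.2.6) and tabulated (SAP 7.6.3).

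**Conclusion.** The point holds, and it is minor. As written, the SAP would leave out of its only laboratory summary any on-treatment marked abnormality seen only on an unscheduled or early-termination test. The protocol's description of that summary contains no such limit.

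The likely number affected is small and may be zero. Participants are healthy, receive single 2.5-mg doses and stay in the clinic until Day 8. Those who stop treatment should still follow the scheduled procedures (Protocol 8.1), and discharge waits until AEs have resolved or are judged not clinically significant (Protocol 9.4.9). The 3.3 points per participant is arithmetic on an assumed denominator of 30, not a forecast.

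The conclusion assumes that the SAP 7.6 exclusion is applied literally and that no unseen sponsor rule overrides it. The primary bioavailability analysis does not use these data and is unaffected.

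**What to change.** **Main change, SAP 7.6.4.** Add: *As an exception to Section 7.6, the marked laboratory abnormality table counts all scheduled and unscheduled results in Periods 1 and 2 (Section 6.1), assigned to the last treatment received. The denominator is treated participants with at least one post-dose result for that treatment. A footnote gives the number whose marked abnormality comes only from unscheduled tests.* If the sponsor guideline or counting rules already do this, cite them here instead.

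Cost: SAP wording and table programming. The drawback is that some for-cause results from an open-label study enter a descriptive table; the footnote keeps them visible.

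**Optional change, Protocol Table 2-2, footnote a.** Add routine laboratory tests at premature discontinuation when that period's Day 4 or Day 7 draw has not been taken and the participant agrees.

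Cost: a minor schedule change and one extra blood and urine sample from the few who leave early, at an evaluation already planned. The yield is limited, because participants who withdraw consent are the least likely to agree.

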7.6.1 Deaths

All deaths reported after a participant is enrolled (ie, has signed the ICF) will be listed for the enrolled population.

7.6.2 Serious Adverse Events

All reported SAEs will be listed for the enrolled population.

7.6.3 Adverse Events

Adverse events that occur on or after the first dose of study treatment will be tabulated. Events will be assigned to the last study treatment administered at the time of onset. Nonserious AEs occurring for up to 3 days after the termination of study treatment and SAEs occurring for up to 30 days after the termination of study treatment will be included in summary statistics. The proportion of participants having an AE will be calculated as the number of participants having the event in the specific treatment interval, divided by the total number of participants receiving study treatment during that treatment interval.

All AE listings will indicate the unique participant identifier, age, gender, current treatment, the date of onset, the date of resolution, day of onset relative to the start of treatment, action taken, investigator's assessment of severity and relationship to study drug. Additional listings will be provided for AEs leading to discontinuation and AEs without recorded resolution.

All AEs will be summarized by system organ class (SOC), preferred term (PT), treatment, and total for the treated population. Summaries of AEs will include AEs, AEs by intensity, and AEs related to study drug.

Adverse Event Counting Rules:

Where a participant has the same AE, based on PT, reported multiple times in a single analysis period, the participant will only be counted once at the PT level in AE frequency tables.

Where a participant has multiple AEs within the same SOC in a single analysis period, the participant will only be counted once at the SOC level in AE frequency tables.

When a participant has the same AE, based on PT, reported multiple times in a single analysis period, the following criteria, in order of precedence, will be used to select the event to be included in summary tables:

- Relationship to study drug
- Intensity of event
- Onset date and time

When reporting AEs by intensity, in addition to providing a summary table based on the event selection criteria detailed above, summary tables will also be provided based on the most intense event during the analysis period, independent of relationship to study medication. For these tables, the following criteria, in order of precedence, will be used to select the event to be included in summary tables:

- Intensity of event
- Onset date and time

Participants will only be counted once in the ‘Total’ at their maximum intensity, regardless of SOC or PT.

7.6.4 Clinical Laboratory Evaluations

The results of all protocol-specified clinical laboratory tests will be listed by participant for the treated population.

Laboratory evaluations will be reported both in conventional units and in International System of Units.

Laboratory results will be classified as markedly abnormal based on sponsor defined criteria. Laboratory results for participants with any marked laboratory abnormality (scheduled and unscheduled) will be listed for the treated population. This listing will include all observations for the specific laboratory test and participant, not only the marked laboratory abnormality measurements. The frequency of participants with any on-treatment marked laboratory abnormality, based on pre-specified criteria, will be presented for the treated population by treatment and total.

7.6.5 Electrocardiograms

All recorded ECGs will be listed for the treated population.

If QT interval corrected for heart rate using Fridericia’s formula (QTcF) is not available in the database, QTcF will be calculated using the reported uncorrected QT Interval and heart rate, and the following formula:

$$QTcF = \frac{QT}{(60/HEART\ RATE)^{1/3}}$$

Participants with ECG intervals outside of a pre-specified range and investigator identified ECG abnormalities will also be listed for the treated population.

The following criteria will be used to determine ECG results that are outside of a pre-specified range:

PR (msec):	Value > 200
QRS (msec):	Value > 120
QT (msec):	Value > 500 or change from baseline > 30
QTcF (msec):	Value > 450 or change from baseline > 30

7.6.6 Vital Signs

Vital signs parameters (systolic blood pressure [BP], diastolic BP, heart rate, respiratory rate, and body temperature) will be listed for the treated population.

Participants with vital signs outside of a pre-specified range will also be listed for the treated population.

The following criteria will be used to determine vital sign results that are outside of a pre-specified range, where changes from baseline are based on matched postural positions and are calculated as parameter value - baseline parameter value:

Heart Rate (bpm)	Value > 100 and change from baseline > 30, or Value < 55 and change from baseline < -15
Systolic BP (mmHg)	Value > 140 and change from baseline > 20, or Value < 90 and change from baseline < -20
Diastolic BP (mmHg)	Value > 90 and change from baseline > 10, or Value < 55 and change from baseline < -10
Respiration (breaths/min)	Value > 16 or change from baseline > 10
Temperature (°C)	Value > 38.3°C or change from baseline > 1.6°C

7.6.7 Physical Examination Findings

All physical examination abnormal findings will be listed per participant and visit for the treated population.

7.7 Pharmacokinetics

The PK population will be used for all PK listings. The Evaluable PK population will be used for summary statistics and statistical analyses. Analysis will include all valid analyte data for apixaban.

Participant plasma concentration-time profiles will be listed and summarized by treatment and nominal collection time for apixaban. Plots of individual plasma concentration profiles over time will be provided. Overlays of individual plasma concentration profiles over time will be provided by treatment. Plots of mean (+SD) plasma concentration profiles versus time will be presented for apixaban, and all treatments will be superimposed on the same plot.

All individual PK parameters will be listed for apixaban including any exclusions and reasons for exclusion. Summary statistics will be tabulated for each PK parameter by treatment. Geometric means and %CV will be presented for C_{max}, AUC(0-T), AUC(INF), and F_{rel}. Medians and ranges will be presented for T_{max}. Means and SDs will be presented for other PK parameters (ie, T-HALF). Decimal place specifications for summary statistics are described in [Section 7.9](#).

A linear mixed effect model with treatment and period as fixed effects and participant as repeated measures will be fitted to the log-transformed PK parameters (C_{max}, AUC[0-T], and AUC[INF]) for use in estimation of effects and construction of CIs. Kenward-Rogers degrees of freedom will be specified in the model. Initial estimation of the variance/covariance will be based on an unstructured (UN) R matrix assuming no common variances or covariances; however, this UN matrix will be assessed and the more parsimonious compound symmetry (CS) R matrix will be imposed if assumptions of common variances and covariances are reasonable and can be supported by the data. Point estimates and 90% CIs will be exponentiated and results will be reported on the original scale.

Specific details with appropriate SAS code are provided below. Apixaban as 0.1-mg sprinkle capsules (Treatment B) is the test treatment and apixaban as 0.5-mg tablets (Treatment A) is the reference treatment in the analysis.

```
PROC MIXED DATA=PKDATA;  
  BY [log transformed PK parameter such as Cmax, AUC(INF), AUC(0-T)];  
  CLASS TREATMENT PERIOD USUBJID;  
  MODEL LOG_PK = PERIOD TREATMENT / SOLUTION DDFM=KR;  
  REPEATED TREATMENT / SUBJECT = USUBJID TYPE = UN R;  
  LSMEANS TREATMENT / CL ALPHA=0.1;  
  ESTIMATE 'B vs. A' TREATMENT -1 1 / E CL ALPHA=0.1;  
RUN; QUIT;
```

Plots of individual treatment ratios of PK parameters (C_{max}, AUC[INF], and AUC[0-T]) combined with geometric least square mean ratios (GMRs) and corresponding 90% CIs from the statistical analysis model, will also be provided. In addition, the GMRs and corresponding 90% CIs for AUC(0-T), AUC(INF), and C_{max} for apixaban will be summarized in forest plots for overall assessment of the relative bioavailability of the test treatment (sprinkle capsules) compared to the reference treatment (tablets).

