10.3.4 Pharmacokinetic Analyses

| Endpoint | Statistical Analysis Methods |
|---|---|
| C _{max} , AUC(INF), and AUC(0-T) | 
Analyses will be performed on the natural logarithms of C_{max}, AUC(INF), and AUC(0-T) using linear mixed-effects model with treatment and period as fixed effects and measurements within participant as repeated measures. Point estimates and 90% CIs for treatment differences on the log scale derived from the model will be exponentiated to obtain estimates for ratios of geometric means and CIs on the original scale.
 
Summary statistics will be tabulated for all PK parameters by treatment. Geometric means and coefficient of variations will be presented for C_{max}, AUC(INF), and AUC(0-T). Individual treatment ratios for PK parameters will be provided in listings and summarized. Plots of individual ratios, geometric least square mean ratios, and corresponding 90% CIs from the statistical analysis model will also be provided. In addition, the geometric mean ratios and corresponding 90% CIs of C_{max}, AUC(INF), and AUC(0-T) will be presented in forest plots.
 |
| T _{max} , T-HALF, and Frel | Summary statistics will be tabulated for all PK parameters by treatment. Arithmetic mean and standard deviation will be presented for T-HALF; median and range will be presented for T _{max} . Individual T _{max} differences will be provided in listings and summarized. Geometric means and coefficient of variations will be presented for Frel. |

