2 STUDY DESCRIPTION

2.1 Study Design

This is a Phase 1, open-label, randomized, 2-period, 2-treatment crossover study in healthy participants. Healthy male or female participants as determined by medical history, physical examination, vital signs, 12-lead electrocardiogram (ECG), and clinical laboratory tests will be

eligible to participate in the study. Participants will undergo screening evaluations to determine eligibility within 28 days prior to study treatment administration. On Day -1, participants will enter the clinical facility and be confined for the duration of the study, until discharge on Day 8. Prior to dosing on Day 1 of Period 1, participants will be randomly assigned to 1 of 2 treatment sequences (AB or BA, where Treatment A is 5 × 0.5-mg apixaban tablets and Treatment B is 25 × 0.1-mg apixaban sprinkle capsules) in a 1:1 ratio. Participants will receive a single oral dose of apixaban on Days 1 and 5. There will be a 4-day washout period between doses. Treatments A and B will be prepared in the pharmacy.

The study design schematic is presented in [Figure 2.1-1](#).

D = Study Discharge; E = Enrollment; R = Randomization; S = Screening; Treatment A = 5 × 0.5-mg apixaban tablets; Treatment B = 25 × 0.1-mg apixaban sprinkle capsules; W = Washout

Physical examinations, vital sign measurements, 12-lead ECG, and clinical laboratory evaluations will be performed at selected times throughout the study. Participants will be closely monitored for adverse events (AEs) throughout the study. Blood samples will be collected for up to 72 hours after study drug administration for pharmacokinetic (PK) analysis. Approximately 240 mL of blood will be drawn from each participant during the study.

Participants will complete a palatability assessment immediately (within 5 minutes) after administration of the apixaban 0.5-mg tablet and 0.1-mg sprinkle capsule dosages, on both Day 1 and Day 5.

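### The primary model omits SEQUENCE and leaves the UN/CS covariance choice until the data are seen, so a post-data choice can slightly move the primary 90% CI

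*SAP*

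**What the plan says.** SAP 2.1 describes a two-period crossover in which "participants will be randomly assigned to 1 of 2 treatment sequences", AB or BA, in a 1:1 ratio. The primary analysis code in SAP 7.7 has "CLASS TREATMENT PERIOD USUBJID" and "MODEL LOG_PK = PERIOD TREATMENT / SOLUTION DDFM=KR", so SEQUENCE is in neither statement. Protocol 10.3.4 agrees, with "treatment and period as fixed effects and measurements within participant as repeated measures". It names no covariance structure.

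The code fits the covariance by treatment, "REPEATED TREATMENT / SUBJECT = USUBJID TYPE = UN R". The text then says that the "compound symmetry (CS) R matrix will be imposed if assumptions of common variances and covariances are reasonable and can be supported by the data". It gives no test, threshold or information criterion. It also does not say whether one choice covers Cmax, AUC(0-T) and AUC(INF) or each is decided separately.

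The result is read from these fits. SAP 5 concludes similarity if the 90% CIs of the B/A ratio lie within 80% to 125%.

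**The concern.** The conclusion depends on where three confidence intervals fall. A model choice made on open-label data, without a written criterion, should not be able to move them. In a complete 2x2 crossover with SEQUENCE in the model it could not, because UN and CS then give the same interval. Leaving out the randomised factor is what lets the choice reach the interval for complete pairs. If a limit fell close to 80% or 125%, the study report would have to defend a choice that the plan did not fix.

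**Working it through.** **Plan's own figure.** Inputs from SAP 5: n = 28, CV 18% for Cmax and 12% for AUC, ratio 1.10, 90% CI within 80-125%.

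- Within-participant SD = sqrt(ln(1 + CV²)): 0.1786 for Cmax, 0.1196 for AUC.
- SE = SD × sqrt(2/28): 0.0477 and 0.0320, with 26 df and t = 1.706.
- Exact power of the two one-sided tests: 83.2% and 98.8%. Product over three parameters: 0.832 × 0.988 × 0.988 = 81.2%. The SAP states 83%, 99% and 81%, so its figures are reproduced.
- For scale, a Cmax ratio observed at 1.10 has half-width 1.706 × 0.0477 = 0.0814 on the log scale and a 90% CI of about 101.4% to 119.3%.

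**Why the printed model differs.** For each participant with both profiles, take on the log scale D = B − A and S = A + B. With period and treatment as the only fixed effects, the mean of D is free in each sequence, but the mean of S is forced to be equal in AB and BA. Generalised least squares then gives

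τ̂ = ½(D̄₁ + D̄₂) − β (S̄₁ − S̄₂)(n₂ − n₁) / [2(n₁ + n₂)], where β = [Var(B) − Var(A)] / Var(S).

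The first term is the standard within-participant estimate. The second term vanishes in three cases:

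- under CS, because Var(A) = Var(B) makes β = 0;
- with SEQUENCE in the model, because the four cell means are saturated and S̄ is no longer constrained;
- when n₁ = n₂, whatever the variances.

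The UN point estimate therefore moves only if the sequence sizes are unequal **and** the estimated treatment variances differ. At 14/14 only the SE and df change, and trivially.

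**Size of the adjustment, variances taken as known.** Assumed between-participant SD 0.30 and within-participant SDs 0.15 and 0.21 (none of these is in the documents):

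- Var(A) = 0.09 + 0.0225 = 0.1125; Var(B) = 0.09 + 0.0441 = 0.1341; Var(S) = 0.1125 + 0.1341 + 2 × 0.09 = 0.4266.
- β = 0.0216/0.4266 = 0.0506.
- At 15/13 the multiplier is −2/56 = −0.0357, and SD(S̄₁ − S̄₂) = sqrt(0.4266 × (1/15 + 1/13)) = 0.2475.
- 95th percentile of the shift: 1.96 × 0.0506 × 0.0357 × 0.2475 = 0.0009 on the log scale, about 0.09%, against a half-width of 0.0814.

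**Variances estimated.** REML with Kenward-Roger df, Cmax CV 18%, true ratio 1.10, between-participant SD about 0.30, UN against CS without SEQUENCE. The 14/14, 15/13 and one-profile shifts come from 20,000 simulated trials per scenario. The pass/fail ranges for complete pairs also cover unequal within-participant SDs and simulation error.

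| Data | Larger CI-limit shift, percentage points (median / 99th percentile / maximum) | Pass/fail differs |
|---|---|---|
| 14/14 complete | 0.002 / about 0.07 / about 0.7 | 0.02-0.07% |
| 15/13 complete | 0.03 / 0.35 / 1.3 | 0.1-0.4% |
| 15/11 complete, within SDs 0.15/0.21 | upper limit moves by at most 1.5% | 0.7% |
| 15/15 with two one-profile participants | 0.08-0.12 / about 0.8 / 2.5-2.9 | about 0.5% |

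With SEQUENCE added, the UN-CS difference is exactly 0 for complete pairs, with 26 df at n = 28. With two one-profile participants it is not removed: pass/fail differs in 0.52-0.65% of trials with SEQUENCE and 0.50-0.54% without.

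**Error rate.** At a true ratio of 1.25, complete pairs, the pass rate is 4.98% at 14/14 for UN, for CS, and for a choice made by likelihood-ratio test. At 15/13 the three are 4.88%, 4.89% and 4.90%.

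**The case against.** The plan is not silent. It names a default (UN), one permitted alternative (CS) and a direction for the switch, so this is an imprecise rule between two structures and not open-ended model selection. Randomisation is 1:1 with 15 per sequence, and Protocol 7.2 lets a replacement take the same treatments, which tends to keep the sequences equal. At equal sizes the point estimate does not move at all. A 15/11 split means 26 evaluable participants, below the plan's target of at least 28. A ratio of 1.10 is also the least favourable row of the power table, where changes of verdict are likeliest. All of this stands, and it is why the point is minor.

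It does not remove the point. Thirty participants are randomised to obtain at least 28 evaluable, so two losses from one sequence give 15/13. Participants discontinued for an AE are not replaced unless the AE is judged unrelated to treatment. SAP 7.9.2 excludes individual profiles, for example when the predose value exceeds 5% of Cmax, and the Evaluable PK definition in SAP 6.3 does not require both periods.

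A reader might infer that omitting SEQUENCE makes the analysis wrong in itself. It does not: CS without SEQUENCE gives the standard crossover answer for complete pairs. A reader might also infer that UN shifts the estimate whenever the treatment variances differ. It does so only if the sequence sizes differ too. Nor would adding SEQUENCE be a complete cure, because it leaves the UN-CS difference in place when some participants contribute one profile.

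**Conclusion.** The point holds as a small gap in pre-specification. The printed model is the only one of the four combinations (UN or CS, with or without SEQUENCE) that departs from the within-participant answer for complete pairs. The plan leaves the move away from it to a judgement after the data are seen. The choice changes pass/fail in well under 1% of simulated trials in every scenario examined: a few in 10,000 when the sequences are equal and complete, and a few in 1,000 when they are unequal or incomplete.

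These sizes rest on an assumed between-participant SD of about 0.30, a true ratio of 1.10 and, in some scenarios, assumed unequal within-participant SDs. For balanced complete data, varying the between-participant CV from 20% to 45% left the rate at about 0.03%.

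The material does not support reading this as bias, an inflated type I error or a power problem. The pass rate at the margin stays just under 5% in the complete-pair scenarios checked, and the stated power and N are unaffected.

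**What to change.** 1. In SAP 7.7, name one covariance structure for all three parameters and delete the sentence that allows CS to replace UN after assessment. This is the necessary part, because it removes the post-data choice in every case, including when some participants contribute one profile.
2. Add SEQUENCE to the SAP code, giving `CLASS SEQUENCE TREATMENT PERIOD USUBJID;` and `MODEL LOG_PK = SEQUENCE PERIOD TREATMENT / SOLUTION DDFM=KR;`, and add sequence to the fixed effects in Protocol 10.3.4. For complete pairs UN and CS then give the same interval.
3. It would also help to state whether participants with only one evaluable profile enter the model, since the two structures still differ for them.

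Cost: one word in each of two statements, a matching phrase in the protocol, one deleted sentence and one clarifying line. The treatment contrast keeps 26 df with 28 complete pairs, so there is no loss of power and no change to the sample size. Priority is low.
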